To address these inequities, our team launched Chama cha MamaToto (Chamas) in 2012 with the Government of Kenya [3,4] (Figure 1). The Chamas program is a group-based, community health volunteer (CHV)-led, peer-support and microfinance program that engages women in pregnancy and the first 1000 days of their child's life. Translated from Kiswahili as 'groups', Chamas are composed of 15-20 women, 2 elders, and 2 government-supported CHVs. Members attend 60–90 min sessions twice monthly. Each session focuses on health, social, and financial topics that have been developed locally and engages group learning through visual and participatory tools. The Year 1 health program focuses on prenatal and perinatal health (e.g., what to expect in prenatal care, benefits of facility delivery, tackling postpartum challenges, exclusive breastfeeding for 6 months, and completing infant immunizations). Years 2 and 3 focus on family planning, parenting skills to foster positive relationships with their children, and strategies to reduce harsh child punishment and alleviate parental stress. Women can decide to join Chamas at any year. Throughout all 3 years, women can engage in a microfinance component that enables them to sustainably finance health practices, enroll in health insurance, start businesses, or meet other family needs. Participation in the group's table-banking is optional so as not to deter women without financial means from joining Chamas.

Chamas aims to recruit the most disadvantaged women in rural and peri-urban communities who face complex and intersecting challenges. The investigators hypothesize that fostering a strong, community-based network through Chamas provides women with the peer support, knowledge, and financial capital that increases their ability to (1) access maternal, newborn, and child health (MNCH) services, (2) improve their socio-economic position, and (3) sustain long-term transformative change (Figure 1).

To test this theory of change, the investigators have carried out successive evaluations leveraging support from county governments and Grand Challenges Canada. The investigators found significant improvements in MNCH outcomes among Chama participants in both our prospective cohort study (2012-2013; n=337) [3] and cluster randomized controlled trial (RCT) (2017-2019; n=1,550) [4]. Chama participants were more likely to engage in behaviours

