associated with improved MNCH outcomes compared to controls [4, 5]. These practices include facility delivery (84.4% vs. 50.4%, $p<0.001$), attending at least 4 antenatal care (ANC) visits (64.0% vs. 37.4%, $p<0.001$), receiving a postnatal care visit <48hrs postpartum (82.0% vs. 47.0%, $p<0.001$), exclusively breastfeeding to 6 months (82.0% vs. 47.0%, $p < 0.001$), and fully immunizing their child at 12 months (91.9% vs. 85.2%, $p=0.41$) [4]. Children of Chama participants had significantly lower rates of at-risk development scores compared to controls [6]. Chama participation also provides much needed social and financial support to CHVs through community recognition, opportunities for skill-building, and contributions from their Chamas. Through ongoing support for Chama implementation from local counties, USAID (see *Letter of Support*) and philanthropic organizations, nearly 300 Chamas have been established with 7,000 women and their children, in 4 counties in western Kenya.

Through stakeholder engagement, the investigators have also implemented Chama cha Babatoto, 'father groups', to facilitate male inclusion and education to shift decision-making authority. In 2019-20, the investigators engaged adolescents to co-design an adapted Chama program to meet their unique needs and are currently completing the first-year implementation with 211 participants in three counties.

The COVID-19 pandemic significantly disrupted women's work and MNCH services globally, due to reallocation of health care resources, fears of COVID-19, transportation restrictions, and lockdowns. A 2022 systematic review from the Gender & COVID Project highlighted the gendered impacts of the pandemic on women's paid and unpaid work in Kenya [7]. Nationwide, two in three adults who lost all their income in 2020 were women. Government responses to economic impacts largely targeted the formal sector, leaving behind women in the informal economy who depend on daily wages. Further, women experienced a disproportionate increase in unpaid care/domestic work, as well as increased gender-based violence and deteriorated mental health. Very little attention has been paid to the effects of the pandemic on CHVs in Kenya, 70% of whom are female globally, despite CHVs facing many of the same economic and gender inequities as those they serve [8].

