For women enrolled in our RCT (pre-pandemic), the baseline mean PPI score was 57 (SD = 21) for all women. Assuming a 0.5 correlation between pre- and post-pandemic PPI measures, the investigators require a total of 444 participants to detect a 5% (2.8 points) change in PPI scores at a significance level of 5% with 80% power. Based on our total recruitment in the RCT (n = 1,550), this should be highly achievable. Using the same standard deviation above, the investigators would need a minimum of 108 participants per cohort to detect an 8-point difference in post-pandemic PPI between the three cohorts. This sample size is highly feasible given the number of women currently within each cohort.

Our secondary outcomes include indicators relevant to MNCH and COVID-19: enrollment in the national health insurance scheme, number of ANC visits attended, facility delivery, maternal death, newborn death, infant death, exclusive breastfeeding, number of children fully immunized

at age 1, attitude towards harsh punishment of children, level of parental stress, COVID-19 infection, COVID-19 vaccination, and effects of COVID restrictions. These data were collected in December 2021 with 1,400 Chama participants across Western Kenya, including 626 from Trans-Nzoia, using an abbreviated version of the validated survey tool from our RCT. Here, the investigators will carry out this survey across the three previously described cohorts of women in early 2023 to understand the effects of Chama participation more fully on these outcomes and quantify the effects of differing levels of PPI and other identity factors on Chama participation and these outcomes.

To obtain the post-pandemic data for women who participated in Chamas, the program's Data Analyst will generate a list of eligible women organized by community unit. CHVs responsible for each unit will locate, obtain consent, and enroll women. Field officers in Trans-Nzoia will oversee 8 local college-level practicum students to work with CHVs in collecting survey data, with each student responsible for a single sub-county. Integrating mentorship of local students in project implementation has been foundational to our engagement in Trans-Nzoia and replicates the data collection model the investigators used successfully for our RCT.

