Focus groups will begin with building trust among participants, ensuring open communication and reducing the likelihood that responses will be impacted by social desirability bias. Interview guides will be developed using the Gender and COVID-19 Matrix and focus on the domains and research questions selected by the local Advisory Group in Aim #1. The investigators will incorporate questions that explore power imbalances related to factors other than gender, and how these factors impacted the response to the pandemic. FGDs and KII will be led by a member of the *Chamas* evaluation team who is experienced in facilitating FGDs and knowledgeable about the *Chamas* model and is of the same sex as the participants to allow for greater comfort among participants. FGDs will be conducted in Kiswahili, audio-recorded, and transcribed for analysis. Transcripts will be translated to English and analyzed using thematic analysis [19]. Preliminary open coding will be conducted by line-by-line reviews of the transcripts to elucidate meanings, processes, and analytical categories. Primary themes will be identified and refined through an iterative process of review, reflection, and re-review of the transcripts. Constant comparison will be used to evaluate how additional data fit with preliminary themes and categories. Once preliminary themes are refined and a category selected to drive a part or the whole theory, axial coding will be conducted to re-analyze the transcripts and re-assemble the data (including developing new codes) around a “core” phenomenon. All analysis will be conducted using Nvivo 12 (QSR International, Melbourne, Australia).

Using a mixed-methods strategy, the investigators will bring the two datasets from the quantitative and qualitative approach in conversation with one another to produce a comprehensive and integrated analysis.

Aim 3: Use an equity-centered design process and narrative approach to share research findings.

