Assumptions: The investigators assume that the financial and peer support of Chamas was protective from the health service disruptions that occurred during the pandemic, and that inclusion in Chamas can continue to facilitate healthy behavior even during health emergencies. The proposed work will provide an opportunity to test this hypothesis. However, the prior research has shown that Chamas provides a safe space and supportive network within which women, regardless of their socioeconomic background, can learn about their reproductive health and right to high-quality and comprehensive care throughout pregnancy and afterwards [3,4]. Within this space they are empowered to demand it together. CHVs who lead Chamas are trained on how to provide quality and respectful care and education, which facilitates women's willingness to seek care.

Financial literacy and skills also contribute to an enabling environment. Access to funds can influence women's decision-making power and break negative cycles of poverty by providing means to access further education and business endeavors that can improve their economic status. This can increase their capacity to access MNCH services [15]. Through men's groups, the investigators will facilitate male inclusion and education to shift decision-making authority and start to break down traditional gender power structures. In addition, parents with more social support report reduced parental stress, which helps buffer children from negative parenting behaviors that can have a long-lasting impact on their development [21].

The storybooks the investigators create in Aim #3 will also directly benefit community members who take part in the co-design process, as they share and reflect upon their own experiences. Narrative storytelling can benefit the storyteller through sharing and helping (by feeling heard & releasing emotions) and re-visiting the story (by reflecting and learning) [20]. The storybooks will also help the families who receive them, as they revisit and reflect upon their own experiences

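### For Chama women, the unit CHVs obtain consent and help collect self-reported outcomes; no procedure is written for control units, so reporting bias may differ by cohort

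*Protocol*

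**What the plan says.** All of this is in the protocol.

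- **Who leads the groups.** Section 2.1 describes the programme as CHV-led: "Chamas are composed of 15-20 women, 2 elders, and 2 government-supported CHVs". Section 3.1 repeats it: "CHVs who lead Chamas are trained on how to provide quality and respectful care and education".
- **What CHVs gain.** Section 2.1 says that Chama participation "provides much needed social and financial support to CHVs through community recognition, opportunities for skill-building, and contributions from their Chamas".
- **What the groups teach.** Section 2.1 lists antenatal care, facility delivery, exclusive breastfeeding, infant immunisation, less harsh punishment and relief of parental stress. The secondary outcomes in section 2.3 include these same items.
- **How the survey is done.** The paragraph in section 2.3 opens with its scope: "To obtain the post-pandemic data for women who participated in Chamas". It then says "CHVs responsible for each unit will locate, obtain consent, and enroll women", and that field officers oversee "8 local college-level practicum students to work with CHVs in collecting survey data".
- **Control women.** The same section says that the survey covers all three cohorts. It describes no consent or interview procedure for women in communities randomised to have no Chamas.
- **Where the bias is recognised.** For the focus groups, section 2.3 speaks of "reducing the likelihood that responses will be impacted by social desirability bias" and has a member of the evaluation team lead them. It states no comparable safeguard for the survey.

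**The concern.** In a cohort comparison based on self-report, the way answers are obtained should not depend on cohort. Here it may. A woman in a Chama unit is asked for consent by a CHV who may have led her group and taught the recommended behaviour, and who has an interest in the programme looking effective. That CHV may then take part in collecting her answers. A control woman either faces a CHV without that tie or is surveyed by an unstated procedure. In both cases measurement may differ between the groups whose contrast is meant to show the effect of Chamas.

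If Chama women lean towards the taught answer more than control women do, part of the observed difference is a reporting artefact. The analysis section plans doubly robust adjustment for confounders, sensitivity analyses for unmeasured confounding and possibly for selection bias. These address who is in each cohort, not whether the outcome is reported equally well in each. A larger sample does not reduce the bias either; it makes a spurious difference more likely to reach significance.

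**Working it through.** **The plan's own figures.** Section 2.3 gives SD 21, correlation 0.5, a 2.8-point change and 444 women in total. The SD of the change is 21 × √(2 × (1 − 0.5)) = 21. Then n = (21 × (1.96 + 0.8416) / 2.8)² = 441.5, so 442 by the normal approximation and 444 by the paired t-test. For 8 points between cohorts, n = 2 × (21 × 2.8016 / 8)² = 108.2 per cohort, against 108 stated. Both reproduce, and neither is in dispute.

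**Illustration for a binary self-reported outcome**

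Inputs from section 2.3: 142 women who stayed in Chamas, 600 who left after 12 March 2020, and 728 in control communities. The quantitative paragraph gives 748 for the last group; using it moves no result below by more than one percentage point.

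Assumed, with no source in the protocol:
- true prevalence p = 0.60 in every cohort, so no real effect;
- a fraction f of Chama women without the behaviour report having it;
- no misreporting in controls;
- no clustering.

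Formulas: observed Chama prevalence p₁ = p + f(1 − p); SE = √(p₁(1 − p₁)/n₁ + p(1 − p)/n₂); z = (p₁ − p)/SE. The chance of a significant result is Φ(z − 1.96) + Φ(−z − 1.96).

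- f = 0.10: p₁ = 0.60 + 0.10 × 0.40 = 0.64. OR = (0.64/0.36)/(0.60/0.40) = 1.19.
- f = 0.20: p₁ = 0.60 + 0.20 × 0.40 = 0.68. OR = (0.68/0.32)/(0.60/0.40) = 1.42.

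| Comparison | f | SE | z | Chance of a false significant result |
|---|---|---|---|---|
| 142 v 728 | 0.10 | 0.0442 | 0.90 | about 15% |
| 142 v 728 | 0.20 | 0.0432 | 1.85 | about 46% |
| 600 v 728 | 0.10 | 0.0267 | 1.50 | about 32% |
| 600 v 728 | 0.20 | 0.0263 | 3.04 | about 86% |

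The nominal rate is 5%. Allowing for clustering would widen the SEs and lower these chances, but would leave the bias in the estimate unchanged.

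**Illustration for post-pandemic PPI**

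SE = 21 × √(1/n₁ + 1/n₂), which is 1.93 points for 142 v 728 and 1.16 for 600 v 728. An assumed differential reporting shift of 2, 3 or 4 points, in either direction, gives a false significant result with chance 18%, 34% or 55% for 142 v 728, and 41%, 74% or 93% for 600 v 728.

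**The case against.** Several objections have force.

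- **The enrolling CHV is not stated to be the woman's own group leader.** A reader might infer that each woman is consented and interviewed by her own Chama leader. The text assigns CHVs by community unit, and the focus-group plan recognises CHVs who did not facilitate Chamas. The overlap is likely but not stated. Working with CHVs to collect data also does not establish that a CHV asks the questions or hears the answers.
- **Most Chama women had left.** Of the 742 women in the two Chama cohorts, 600 (81%) left after 12 March 2020. For them the CHV is at most a former leader, and any deference may be weaker. The 600 v 728 rows may therefore assume too much over-reporting. Pooling all 742 against controls would not match the planned three-cohort comparison, so it is not done here.
- **Some bias may be shared.** CHVs also work in communities without Chamas. If they take part in the survey there, control women too may give the approved answer, and the difference between cohorts shrinks.
- **The primary outcome is less exposed.** A reader might infer that the primary result is compromised. It is an overall pre-post change in PPI, and the survey repeats the data-collection model of the RCT, so a constant reporting bias could partly cancel.
- **Interview privacy is a field-manual matter.** That is partly fair. But the protocol itself fixes who obtains consent and who helps collect the data, and it fixes this for the Chama women only.

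These points limit the claim to a risk to particular comparisons. They do not remove it, because nothing in the plan makes the survey procedure the same across cohorts or separates the Chama CHVs from the answers.

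**Conclusion.** The concern holds as a risk of differential misreporting. It bears on the between-cohort comparisons of self-reported secondary outcomes that overlap with Chama teaching: breastfeeding, attitude to punishment, parental stress, antenatal visits and immunisation. It bears on the post-pandemic PPI comparison too, where answers about poverty could shift either way.

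The protocol does not show that such bias will occur, how large it would be, or that it must favour Chamas. Over-reporting of taught behaviours is the plausible direction, not an established one. The tabulated chances rest on assumed over-reporting rates, an assumed prevalence of 60%, no misreporting in controls and no clustering. They show that modest differential misreporting would matter at these cohort sizes; they are not forecasts. The change is worth making because it is cheap and no planned analysis can substitute for it.

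**What to change.** In the survey paragraph of section 2.3:

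- limit CHVs to locating women and introducing them to the study team;
- have the practicum students already in the plan obtain consent and administer the questionnaire in private, without the CHV present;
- state that this identical procedure applies in all three cohorts, including the control units.

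Cost: no new staff, but the students need training in consent and take on somewhat more field time. At full recruitment the load is (142 + 600 + 728)/8 = 1,470/8, or about 184 women per student for consent and interview. CHVs keep their part in finding women and making the introduction, so the community-based approach is largely preserved, although interviews may be slightly slower to arrange.

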2.2 Overall and specific objectives of the project

Our overall objective is to use a participatory design approach to understand how participation in Chamas, a program that aims to improve MNCH and reduce gender and social inequities, intersected with other factors to mitigate the effects of the COVID-19 pandemic on women's and children's health and economic well-being.

The investigators anticipate using the findings to guide the scale-up of the Chama program and ensure it not only improves the health and well-being of women, but simultaneously strengthens equitable recovery, gender-transformative policies, and local preparedness to future health emergencies, as outlined by the Women RISE objectives.

To carry this out, the investigators will:

1. Establish a platform for participatory and collaborative decision-making on the design and implementation of the proposed evaluation.
2. Evaluate the effect of Chama participation on mitigating the effects of the pandemic on social and gender equity using a mixed-methods approach.
3. Use an equity-centered design process and narrative approach to share research findings.

Increasingly, it is argued that research fails to adopt an equity lens in global health, especially when the methods of data collection and extraction are solely determined by the researchers. To address this, the investigators propose to integrate participatory action-based methods throughout this proposal.

Further, as gender is not the only factor that influences a person's experience of COVID-19 and government responses, the investigators will use an intersectional feminist perspective to consider the complex interactions between structures of power and the interconnected aspects of individual and group identity such as age, occupation, marital status, poverty level, education, health insurance, chama participation, household size, community unit. The investigators will aim to capture gender dimensions by disaggregating outcomes of interest by sex and explore the intersecting axes of power and economic status by disaggregating data by age, poverty level, and other identified factors.

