2.3 Methodology

Study Timeline: See Figure 2.

Study Design: The investigators will use a mixed-methods strategy using quantitative and qualitative approaches, leveraging cohorts from our RCT completed in Trans-Nzoia County (2017-2019). The investigators have selected a mixed-methods approach based on our experience that it provides a pragmatic approach to exploring complex social processes. The investigators have drawn on best practices from intersectionality-informed mixed methods research to guide this proposal [11].

Study Site: This study will be carried out in Trans-Nzoia County, where the investigators have longstanding partnership in HIV and MNCH care, including Chama implementation (see *Memorandum of Understanding in Policy Documents*). Trans-Nzoia has a population of 990,341 with 489,107 women and 129,558 children under-five [12]. During the RCT, women were recruited from public health facilities linked to any of the 77 community units (CUs) in 4 sub-counties (Saboti, Kiminini, Cherangany, and Kwanza). These sub-counties primarily subsist on agriculture and livestock farming, with increasing numbers of agricultural and small businesses. Kitale (in Saboti sub-county) is urban, Kiminini is peri-urban, and Cherangany and Kwanza are rural.

Health outcomes in Trans-Nzoia vary between sub-counties but are poor overall. Only 56% of children are fully immunized at age 1, and 58% of women deliver in facilities. The infant mortality rate is 58 per 1,000 livebirths compared to a national average of 39 per 1,000 [13]. Only 29% of women use family planning compared to a national average of 58% [13].

Study Population:

- (1) Women from the RCT who participated in Chamas throughout the pandemic (n=142).
- (2) Women who left Chamas after Mar 12, 2020, the day the first case of COVID-19 was detected in Kenya (n=600).
- (3) Women whose communities were randomized to not implement Chamas during the RCT (n=728).
- (4) CHVs in communities who either did or did not have Chamas operating during the pandemic.
- (5) County health officials.
- (6) Fathers participating in Chama cha Babatoto.
- (7) Adolescent girls currently participating in Chamas adapted for adolescents (15 to 24 years of age; enrolment after Jan 2022).

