Our recently completed RCT [4] uniquely positions our team to provide fine-grained empirical data about women's experiences of the pandemic as the investigators have a robust research infrastructure and strong linkages with the communities that participated in the trial. Following the completion of the RCT, the investigators planned to scale-up the program throughout Trans-Nzoia. This scale-up was put on hold due to the pandemic. As a result, there are now multiple groups of women in communities that are well positioned to share to what extent participating in Chamas helped mitigate the effects of the pandemic and related restrictions. Further, the investigators have the ability to compare this to the experiences of those women in the community units where Chamas have not yet been implemented.

Quantitative Data Collection and Analysis: The investigators will quantify the impacts of the pandemic on economic status and health service utilization among women in Trans-Nzoia, focusing on the first 3 study cohorts described above: (1) women who participated in Chamas throughout the pandemic (n=142), (2) women who left Chamas during the pandemic (n=600), (3) women whose communities were randomized to not receive the Chamas intervention (n=748). Our primary outcome will be the change in the mean 2015 Kenya PPI score pre- and post-pandemic for the study participants. The PPI is calculated using a validated set of 10 simple, easy-to-answer questions and estimates the likelihood the participant is living below the national poverty line, or other internationally recognized poverty lines [14]. Each response is given a value, and the total value of all the answers is the participant's PPI score. The PPI "look-up table" for Kenya will then be used to convert the PPI score to a likelihood of the respondent's household being below a poverty line. The investigators will also compare the PPI at the post-pandemic period between three cohorts. The investigators have chosen this as our primary outcome because, from an equity perspective, poor MNCH outcomes are disproportionate across socioeconomic strata. Access to care is generally correlated with economic accessibility and women of lower socioeconomic status often encounter greater barriers to accessing high quality care [14, 16]. The investigators have also chosen this variable as it is meaningful to the county government.

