First, the investigators will summarize descriptive data for the PPI and MNCH characteristics pre- and post-pandemic, as well as by each of the three cohorts specified above. To assess the overall change in PPI post-pandemic the investigators will use a linear mixed effects model adjusted for relevant baseline covariates to estimate the mean difference in PPI from pre to post. Second, the investigators will assess the relationship between sociodemographic variables (e.g., PPI, education, age) and health outcomes (e.g., health insurance status, ANC visits). The investigators will do this both overall by time period as well as disaggregated by cohort by including interactions between sociodemographic variables and cohort group. Results will be presented as cohort specific estimates (e.g., odds ratios for binary outcomes) as well as predicted probabilities of health outcomes by group. All models will account for clustering of data by sub-county using random effects and, when available, the investigators will adjust for relevant sub-county-level indicators. Exploratory analysis will include correlation between outcomes (by group) and reported COVID-19 cases.

When comparing each of the three cohorts the investigators will consider several approaches to adjust for possible confounding, as those who remain in Chamas may differ from those who did not. Confounders will be identified based on expert input and previous literature and adjusted for using doubly robust methods for causal inference, such as combining inverse probability weighting and standard regression, or via targeted maximum likelihood estimation [17, 18]. Sensitivity analyses for unmeasured confounding will be conducted and the investigators may consider further sensitivity analyses to assess impact of possible selection biases depending on the level of follow-up achieved from the original cohort(s) [18].

Qualitative Data Collection and Analysis: While the quantitative dataset will provide information on the impact of COVID on health service utilization and economic status, the investigators will draw on a qualitative approach to put these findings in context and specifically explore gender dynamics as social processes. The investigators will conduct focus group discussions (FGDs)

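### Every model clusters on the 4 sub-counties and no lower level, yet cohort 3 was set by randomising communities, so standard errors for contrasts with cohort 3 are too small if women within a community are correlated

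*Protocol*

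**What the plan says.** The protocol's quantitative analysis text (Section 2.3, Aim 2) sets one clustering level for everything: "All models will account for clustering of data by sub-county using random effects". Sub-county-level indicators may be added where available. The next paragraph says that confounding in the cohort comparisons will be "adjusted for using doubly robust methods for causal inference, such as combining inverse probability weighting and standard regression", or by targeted maximum likelihood. It names no clustering unit for the variance of those estimates.

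The design information lies elsewhere in the protocol:

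- Section 2.1 describes the parent study as a cluster randomised trial of 1,550 women.
- Section 2.3, Study Site, says "women were recruited from public health facilities linked to any of the 77 community units (CUs) in 4 sub-counties".
- Section 2.3, Study Population, defines cohort 3 as "Women whose communities were randomized to not implement Chamas during the RCT (n=728". The Aim 2 text gives 748 for the same cohort.
- Section 2.3, Aim 2, describes the comparison women as "those women in the community units where Chamas have not yet been implemented".
- Section 2.2 includes community unit in its list of identity factors ("health insurance, chama participation, household size, community unit"), but not as a level of clustering.

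The protocol does not say whether the community unit was the unit randomised, how many units were randomised, or how they were split.

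**The concern.** Membership of cohort 3 is constant within a community. In a contrast with cohort 3, differences between communities add directly to the error of the estimate, and the number of communities limits how far that error can be averaged out. An intercept for each of 4 sub-counties cannot absorb variation between communities inside a sub-county. That variation goes into the residual and is averaged over women as if each were independent.

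The plan says: "The investigators will also compare the PPI at the post-pandemic period between three cohorts". Cohort 3 is the only group without Chamas, so these contrasts carry the question of whether Chamas softened the effects of the pandemic. With standard errors too small, ordinary differences between communities can be reported as a Chama effect, mainly in cohort 2 vs 3.

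**Working it through.** **Inputs from the protocol (Section 2.3).** Cohort sizes 142, 600 and 728 (748 in a second place); PPI standard deviation 21; 77 community units in 4 sub-counties.

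**Assumptions.** ICC of 0.01, 0.02, 0.05 or 0.10 (none is stated); 77 units split evenly, so k = 38.5 per arm; women spread evenly over units; no covariates. For a given number of units, an even spread of women gives the smallest design effect.

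**Step 1: the plan's own sample sizes.** For an 8-point difference between cohorts, n = 2 × (1.960 + 0.842)² × 21² / 8² = 108.2, against 108 stated. For the pre/post change, the SD of the difference is 21 × √(2 × (1 − 0.5)) = 21. Then n = (1.960 + 0.842)² × 21² / 2.8² = 441.5, or 444 with the t distribution, as stated. Both reproduce only as independent-observation formulas, with no allowance for clustering.

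**Step 2: design effect of a cohort contrast.**

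DE = [(1 + (n₁/k₁ − 1) × ICC)/n₁ + (1 + (n₂/k₂ − 1) × ICC)/n₂] / (1/n₁ + 1/n₂)

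True size of a nominal 5% test = 2 × Φ(−1.96/√DE)

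95% half-width = 1.96 × 21 × √(1/n₁ + 1/n₂) × √DE, with DE = 1 when community is ignored.

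Example, 2 vs 3 at ICC 0.01: women per unit are 600/38.5 = 15.58 and 728/38.5 = 18.91. DE = (1.1458/600 + 1.1791/728) / (1/600 + 1/728) = 1.161, √DE = 1.077, size = 2 × Φ(−1.96/1.077) = 6.9%.

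| Contrast | ICC | DE | √DE | True size | Half-width, community ignored | Half-width, correct |
|---|---|---|---|---|---|---|
| 2 vs 3 (600 vs 728) | 0.01 | 1.161 | 1.08 | 6.9% | 2.27 | 2.45 |
| | 0.02 | 1.322 | 1.15 | 8.8% | 2.27 | 2.61 |
| | 0.05 | 1.804 | 1.34 | 14.5% | 2.27 | 3.05 |
| | 0.10 | 2.609 | 1.62 | 22.5% | 2.27 | 3.67 |
| 1 vs 3 (142 vs 728) | 0.01 | 1.052 | 1.03 | 5.6% | 3.78 | 3.87 |
| | 0.02 | 1.103 | 1.05 | 6.2% | 3.78 | 3.97 |
| | 0.05 | 1.259 | 1.12 | 8.1% | 3.78 | 4.24 |
| | 0.10 | 1.517 | 1.23 | 11.2% | 3.78 | 4.65 |

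**Step 3: sensitivity of the true size (ICC 0.01/0.02/0.05/0.10).**

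| Change | 2 vs 3 | 1 vs 3 |
|---|---|---|
| 748 in cohort 3 | within 0.2 points of the table above | within 0.2 points |
| 77 units split 26/51 | 7.1/9.3/15.6/24.2% | 5.7/6.4/8.5/12.0% |
| 40 units split evenly | 8.8/12.6/22.4/33.8% | 6.3/7.6/11.5/17.5% |
| Half of each cohort followed up | 5.9/6.8/9.5/13.9% | 5.2/5.5/6.2/7.5% |

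With only the stated minimum of 108 women in each of two cohorts, the size is 5.2/5.4/6.1/7.1%.

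**Step 4: simulation of the models.** 77 units in 4 sub-counties, sub-county variance share 0.01.

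- *Mixed model (REML, 3,000 datasets per cell; Monte Carlo error 0.4 points at 5%).* With a sub-county random intercept only, size is 7.7/9.7/15.0/22.3% for 2 vs 3 and 5.2/6.8/8.2/12.3% for 1 vs 3. At ICC 0 it is 4.6% and 4.3%. Adding a community-unit random intercept brings every cell to 4.0–5.9%.
- *Separate simulation with sub-county as fixed terms (4,000 datasets per ICC).* 6.6/8.1/15.5/23.2% for 2 vs 3 and 5.2/6.5/8.2/12.9% for 1 vs 3. Cohort 1 vs 2 stays between 4% and 5%.
- *Doubly robust estimator (augmented inverse probability weighting, 10,000 datasets per cell, ICC taken after adjustment).* With unclustered variance, 6.7/9.1/14.3/23.0% and 5.7/7.0/9.2/12.9%. With variance summed by community unit, 5.4–6.4%.

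**The case against.** The strongest reply has five parts.

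*The sentence does not exclude other levels.* The pre/post mixed model also needs a within-woman term that is not named, so the sentence is not a full list of random effects, and an analysis plan could add a community level. That is possible. Even so, the protocol chose a level for all models and chose one too high. An analyst who follows it gets the wrong standard errors.

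*The headline sizes assume every listed woman is surveyed.* This stands as a limit on size. The protocol itself foresees incomplete follow-up, and at half follow-up the 2 vs 3 range falls to 5.9–13.9%. The 40-unit case is illustrative and has no basis in the protocol.

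*The doubly robust figures rest on an unclustered variance that the protocol does not specify.* This is also fair. They show what happens if community is ignored there, and that doubly robust adjustment for confounding does not by itself repair the variance.

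*The reach is limited.* The primary pre/post change is not covered. For 1 vs 3 the effect at ICC 0.01 cannot be told from 5% in simulation. All figures are for differences in mean PPI. The health-outcome models estimate sociodemographic associations and their interactions with cohort; those covariates vary within communities, so the figures do not carry over to them directly.

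*The 8-point target is still detectable.* With full cohorts and ICC 0.10, power for 8 points is about 99% for 2 vs 3 and 92% for 1 vs 3. The risk is thus false claims about smaller differences, not missed large ones.

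**Conclusion.** The concern holds. The clustering rule as written gives standard errors that are too small for contrasts with cohort 3 whenever women in the same community are positively correlated. The direction follows from the design. The size depends on an ICC, a number of randomised units and a follow-up rate that the protocol does not give.

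Under the base assumptions, the standard error for 2 vs 3 is understated by about 7% at ICC 0.01 (1 − 1/1.077) and 38% at ICC 0.10 (1 − 1/1.615). For 1 vs 3 the understatement is about 3% to 19%, negligible at the low end. Covariates that explain community differences reduce the problem in proportion: halving the ICC halves the excess of the design effect over 1. The point should be fixed, chiefly for cohort 2 vs 3.

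**What to change.** Replace the clustering sentence in Section 2.3 with wording such as:

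> All models comparing cohorts will include a random intercept for the unit of randomisation in the parent RCT (community or community unit), in addition to sub-county, and variance for the doubly robust cohort comparisons will be clustered on that unit.

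State what that unit was and how many were randomised. Take the identifiers for cohort 3 from the parent trial's allocation records, because Section 2.3 describes the field list by community unit only for women who took part in Chamas. Whether sub-county is fixed or random can be left to the trial statistician, and the planned sub-county-level indicators can stay.

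The cost is one sentence, the linkage, and wider intervals. In simulation the standard error grows by a factor of 1.08–1.62 for 2 vs 3 and 1.04–1.26 for 1 vs 3 over ICC 0.01–0.10. If the ICC is truly 0, the extra term costs about 3% and 1% in standard error.
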